**Research Protocol Abstract:**

Placement of labor epidurals is a very common daily practice in obstetrical anesthesia. Currently, these epidurals are placed based upon palpation of landmarks to determine midline and the correct spinal level for placement. Palpation of these landmarks can be difficult, however, particularly in morbidly obese patients who have significant amounts of soft tissue overlying these landmarks which can contribute to an increased number of attempts needed for placement, increased time required to complete the procedure, increased likelihood for complications, and decreased patient satisfaction. In recent years, ultrasound guidance has been increasing in popularity as a way to help visualize the spine and offset these challenges, though there is a lack of data comparing its practical application for daily use against the current standard of a palpation based only technique.

**Objectives:**

The objective of this study is to determine if ultrasound guidance can be utilized in morbidly obese patients to improve the total time required for epidural placement, decrease the number of attempts needed, increase the success rate in the first attempt, decrease the complication rate, and lead to improved patient comfort and satisfaction levels.

**Study Design:**

Prospective, multicenter (MWH and West Penn Hospital) randomized controlled trial

**Setting/Participants:**

This study will be limited to inpatient laboring patients presenting to Magee Women's Hospital of UPMC and to West Penn Hospital and desiring epidural anesthesia for anticipated vaginal delivery. Inclusion criteria include BMI  $\geq 40$ , Age  $\geq 18$ , and ASA classification score of 3. Exclusion criteria include contraindications to neuraxial blockade, previous lumbar surgery, intrauterine fetal demise, non-viable fetus, or known scoliosis.

**Study Interventions and Measures:**

The major intervention in this study is the use of ultrasound (US) guidance to assess for correct spinal location prior to epidural placement. This differs from the current standard of care which is to use palpation only to assess for correct spinal location. The outcome measures that will be assessed and evaluated include:

- Total time required for epidural placement\*
- Epidural procedure time\*\*
- Number of epidural attempts needed
- Success rate in the first attempt
- Complication rate including incidence of PDPH and paresthesias
- Incidence of failed epidurals needing to be replaced
- Verbalized patient anxiety and satisfaction levels based on a 1-10 scale
- Modified Woman's Views of Birth Labour Satisfaction Questionnaire (WOMBLSQ) scores

\*Procedure time plus the time needed to locate the puncture site using either palpation or ultrasound guidance, begins when hands or ultrasound probe are applied to the patient

\*\*Time from insertion of the epidural needle to removal of the epidural needle

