**Secondary Objectives (or Aim)**

The secondary objectives are to further determine if using ultrasound guidance for epidural placement:

- Decreases the number of attempts
- Increases the success rate in the first attempt
- Decreases the number of failed epidurals
- Leads to fewer complications including PDPH or paresthesias
- Improves patient satisfaction and anxiety levels

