This study is to be a prospective, randomized, controlled trial of morbidly obese parturients presenting to either West Penn Hospital or Magee Women's Hospital for delivery and desiring epidural anesthesia. Patients will be screened for participation in the study during the standard pre-anesthesia assessment that is already conducted by anesthesia staff on all patients presenting to Labor and Delivery. Screening will include an evaluation of the patient's medical history and BMI. The study will then be explained to patients who satisfy the inclusion and exclusion criteria and informed consent obtained should they choose to participate. A waiting period of 5-30 minutes will elapse between introduction of the study to the participant's consent to participate. At the time the patient is ready to receive their epidural, an opaque, sealed, numeric envelope labeled only with a study number will be opened containing the data collection sheet and randomly assigned group for that participant. These envelopes will be prepared prior to beginning the study by a healthcare provider not involved in the study. An online randomizer (Randomization.org) will be used to generate a random order for assignment to either the ultrasound guidance group (experimental group) or the palpation only group (control group) which will be revealed to the experimenters only upon opening the envelope at the time of epidural request. These envelopes will be distributed in equal numbers to each facility participating in the study at the onset of the study.

Once the patient has progressed in their labor to the point where they request placement of labor epidural analgesia, the primary investigator for that site ([name] at Magee, and [name] and West Penn) will be the one to open the envelope revealing which group the patient has been assigned to. This will occur during the same hospitalization as the screening visit and in many cases within just a matter of minutes to hours after the initial screening and consent process. This same person will then position the patient in

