their labor and delivery room appropriately for their epidural and then use either the ultrasound machine (experimental group) or palpation (control group) to mark with a marking pen the desired location for epidural placement. [name] and [name] will be the only providers to mark the patients. Every attempt will be made for them to be available for study patients, but if they cannot be (they are caring for another patient or are no longer in the hospital at the time the epidural is requested) then the patient may have to be dropped from the study. Once the patient has been marked, a second anesthesia provider who will be performing the epidural will come into the room. This second provider will be blinded to whether the marks on the patient were made based upon ultrasound guidance or palpation (the patient will not be blinded). This second provider who will perform the epidural can be any type of experienced provider (attending, fellow, resident, or CRNA) who has already completed at least 40 epidurals in the past. They will then perform the epidural in the standard fashion, using the previously marked site as their initial entry point. If entering at the already marked site does not result in success, the provider performing the procedure may reassess and redirect at their discretion. During epidural placement, the primary investigator ([name] or [name]) will be responsible for timing the procedure and recording the number of attempts required to succeed. Epidurals are typically placed successfully within 5-10 minutes depending on patient anatomy and provider experience.

Following the epidural placement and achievement of pain relief, the patient will be asked to rate their satisfaction and anxiety levels during the procedure. No extra interventions or monitoring specific to this study (i.e. outside of what is already normally performed) will be required.

Patients will be followed up on in their hospital room within 24 hours of their delivery to assess for any complications related to their epidural placement and to administer the modified WOMBLSQ questionnaire. If a complication is detected, treatment will be given as clinically warranted. Following that visit no further participation from the patient will be necessary. This study is projected to take about 6 months to complete.

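### Satisfaction and anxiety are spoken 1-10 ratings from an unblinded woman to an unnamed asker; a sealed self-completed card would reduce reporting bias cheaply (minor, secondary outcomes only)

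*Protocol*

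**What the plan says.** The protocol's Study Interventions and Measures section gives the mode of collection: "Verbalized patient anxiety and satisfaction levels based on a 1-10 scale". The Secondary Objectives section makes the result a stated aim: "Improves patient satisfaction and anxiety levels".

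The description of research activities sets out who is present and who knows what:

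- The site's primary investigator "will be the one to open the envelope revealing which group the patient has been assigned to". The same person marks the insertion site, times the procedure and counts the attempts.
- The operator comes in afterwards: "This second provider will be blinded to whether the marks on the patient were made based upon ultrasound guidance or palpation".
- In the same sentence, in parentheses: "the patient will not be blinded".
- On timing: "Following the epidural placement and achievement of pain relief, the patient will be asked to rate" her satisfaction and anxiety. The wording is passive, and the follow-up section repeats it in the same form. Neither place names the person who asks or records.

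The patient is visited within a day of delivery to check for complications and "to administer the modified WOMBLSQ questionnaire". Neither the person who gives the questionnaire nor the mode (interview or self-completed) is stated.

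The SAP sets one general significance threshold, P ≤ 0.05, and has no separate provision for patient-reported outcomes.

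**The concern.** The design takes care to keep the operator unaware of how the mark was made. It gives the patient-reported outcomes no comparable protection. A woman who knows whether ultrasound was used gives her score aloud, and no step keeps that score from the person who knows her allocation or from the person who has just placed the epidural.

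Two different effects could follow, and they should be kept apart:

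- **Compression.** Politeness toward staff pushes scores in both arms toward the favourable end. This does not create a difference, but it can hide a real one.
- **Differential shift.** If the asker knows the arm, tone or phrasing may differ between arms, and so may the answer. This can create a difference where there is none, or mask one.

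At stake is one secondary aim. The protocol's Significance section counts patient satisfaction among the practical aspects on which the investigators hope to support more routine use of ultrasound. A satisfaction benefit collected this way would be open to challenge, and no later analysis could separate reporting bias from real benefit.

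**Working it through.** **Step 1. Who could hear the score.**

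| Person | Knows the arm? | Role | Named as the asker? |
|---|---|---|---|
| Patient | Yes | Gives the rating | – |
| Site investigator | Yes, opened the envelope | Marks, times, counts attempts | No |
| Operator | Blinded to the marking method | Places the epidural | No |
| Anyone else | Not described | Not described | No |

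The asker is unspecified. If it is the investigator, both effects are possible. If it is the operator, courtesy is possible, but knowledge of the arm does not enter through the asker unless the woman reveals it. If it is an independent person unaware of the arm, both effects are smaller. The documents do not exclude any of these.

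**Step 2. Equal courtesy.** If speaking aloud adds the same amount c to both arms, the difference is (μ₁ + c) − (μ₀ + c) = μ₁ − μ₀. It is unchanged, and with no true effect the false-positive rate stays at 5%. Only a ceiling on the scale alters the comparison, and it does so by shrinking a real difference.

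**Step 3. Differential shift, as illustration.** The plan has no figure to reproduce: it gives no rating SD, no shift and no sample size. The SAP says that the sample size will come from pilot data, with 80% power for a six-minute difference at two-sided alpha 0.05.

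*Assumed range of sizes.* n per arm = 2(1.960 + 0.842)² × SD² / 6², rounded up. Assumed SDs of 6, 8, 10 and 12 minutes for total time give 16, 28, 44 and 63 per arm.

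*Rejection probability with no true effect and a spurious shift b* (normal approximation):

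SE = SD × √(2/n); P = Φ(b/SE − 1.96) + Φ(−b/SE − 1.96)

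Worked case: n = 16, SD = 2, b = 0.5. SE = 2 × √(2/16) = 0.707 and b/SE = 0.707, so P = Φ(−1.253) + Φ(−2.667) = 0.105 + 0.004 = 0.109.

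| n per arm | b = 0 | b = 0.5, SD 2 | b = 0.5, SD 2.5 | b = 1, SD 2 | b = 1, SD 2.5 |
|---|---|---|---|---|---|
| 16 | 5.0% | 10.9% | 8.7% | 29.3% | 20.5% |
| 28 | 5.0% | 15.5% | 11.6% | 46.5% | 32.2% |
| 44 | 5.0% | 21.6% | 15.5% | 65.0% | 46.7% |
| 63 | 5.0% | 28.9% | 20.2% | 80.1% | 61.2% |

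The rating SD, the shift and the per-arm sizes are all assumptions. The table shows how sensitive the comparison would be to a differential shift. It does not show that one would occur, nor how much of it would come from speaking aloud rather than from the woman knowing her arm.

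**The case against.** The case on the other side is substantial, and most of it stands as a limit on the point.

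- **A reader might infer that the scores are spoken to the staff treating her.** The documents do not say so. The finding is that the asker is unnamed and that nothing rules the investigator or operator out.
- **The operator is blinded to the marking method.** This is a real safeguard. It confines the route through the asker's knowledge to the case where the investigator, or someone else aware of the arm, takes the score. It does not remove courtesy toward the person who has just done the procedure.
- **A reader might infer that courtesy by itself biases the comparison.** It does not when it is equal in both arms. The same site investigator marks and attends in both arms, so equal courtesy is at least as plausible as unequal.
- **The percentages cannot be tied to this trial.** Correct: they are illustrative only.
- **A reader might infer that the WOMBLSQ is read aloud too.** To administer a questionnaire does not imply an interview, and it may already be self-completed. The mode is simply unstated.
- **Open allocation is the larger problem, and a card does not touch it.** Correct. The card reduces one component of the bias.

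None of this answers the remaining point: the stated mode is spoken, no concealment of the score is described, and a better mode is available at little cost.

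**Conclusion.** The concern holds as a minor one. The protocol specifies spoken ratings from an unblinded woman, leaves the asker unnamed, and describes no step that keeps the score from the investigator who knows the arm. Compression in both arms, or a differential shift if the asker knows the arm, is therefore possible in a stated secondary aim.

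The size is unknown. Under the assumptions shown (shift 0.5 point, rating SD 2 to 2.5, 16 to 63 per arm), the false-positive rate would be about 9% to 29% instead of 5%. Without a differential shift or a ceiling effect it stays at 5%.

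The documents do not support saying that the satisfaction result will be biased. The primary outcome, total time to placement, is not patient-reported and is unaffected. This is a cheap improvement, not a flaw that threatens the trial.

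**What to change.** Amend the protocol in three places: Study Interventions and Measures, the description of research activities, and the follow-up procedures.

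1. Replace the verbalised rating with a written 1-10 card for satisfaction and anxiety. The woman completes it herself and seals it in a fresh envelope, which is opened only at data entry. The allocation envelope has already been opened and should not be reused.
2. Where a woman cannot write, allow a spoken answer and flag it on the data sheet.
3. State that the modified WOMBLSQ is self-completed and returned sealed in the same way.

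If spoken ratings are kept, name a collector who is outside her care and unaware of the arm.

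Cost: a card and an envelope per woman, a second envelope for the WOMBLSQ, and a sentence or two in each section. The card route needs no extra staff; an independent collector might. The documents give no costing. The downside is probably a few more blank or illegible answers than with a spoken rating. Expectation bias from open allocation remains, and the report should say so when it presents these outcomes.

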**Describe the availability of resources and the adequacy of the facilities to conduct this study:**

\* The facilities and resources as they currently exist are perfectly adequate for this study. This study involves performing epidurals on laboring inpatients at Magee Women's Hospital which is already routinely done many times every day. All of the supplies and resources necessary are already present. The study also involves using an ultrasound machine to evaluate the patient's spine prior to performing the epidural. Such an ultrasound machine is already owned by the anesthesia department and resides on the labor and delivery floor to be used to help with epidurals and other various procedures. We have every ability to use this machine for this study at no additional costs to the patients, anesthesia department, or hospital. Everything we need, we already own and are able to use. No additional resources, expenses, or charges will be needed as a result of this study.

**Objective: What is the overall purpose of this research study? (Limit response to 1-2 sentences.)**

The objectives of this study are to assess if using ultrasound imaging to identify the epidural space prior to epidural placement in morbidly obese patients improves results over a palpation based technique alone in regards to:

- Epidural procedure time
- Total time
- Number of attempts
- Success rate in the first attempt
- Number of failed epidurals
- Complications including post dural puncture headache (PDPH) or paresthesias
- Patient anxiety and satisfaction levels

**Specific Aims: List the goals of the proposed study (e.g., describe the relevant hypotheses or the specific problems or issues that will be addressed by the study).**

**Primary Objective (or Aim)**

The primary objective of this study is to determine if using ultrasound guidance for epidural catheter placement is associated with a reduction in the total time required in epidural catheter placement.

**Secondary Objectives (or Aim)**

The secondary objectives are to further determine if using ultrasound guidance for epidural placement:

- Decreases the number of attempts
- Increases the success rate in the first attempt
- Decreases the number of failed epidurals
- Leads to fewer complications including PDPH or paresthesias
- Improves patient satisfaction and anxiety levels

**Background: Briefly describe previous findings or observations that provide the background leading to this proposal.**

Placement of labor epidurals is a very common daily practice in obstetrical anesthesia. Currently, these epidurals are placed based upon palpation of landmarks to determine midline and the correct spinal level for placement. Palpation of these landmarks can be difficult, however, particularly in morbidly obese patients who have significant amounts of soft tissue overlying these landmarks which can contribute to an increased number of attempts needed for placement, increased time required to complete the procedure, increased likelihood for complications, and decreased patient satisfaction. In recent years, ultrasound guidance has been increasing in popularity as a way to help visualize the spine and offset these challenges.

Ultrasound guidance is already used in multiple patient populations to assist with many different procedures including neuraxial and peripheral nerve blocks. With regards to peripheral nerve blocks, it is now considered standard of care to use ultrasound guidance to provide visualization when performing nearly any procedure including interscalene blocks, supraclavicular blocks, infraclavicular blocks, axillary blocks, femoral nerve blocks, sciatic nerve blocks, adductor canal blocks, quadratus lumborum blocks, transversus abdominus plane blocks, and others. It is also standard in anesthesiology to use ultrasound guidance to assist with central line placement such as internal jugular or femoral vein central lines. Multiple centers have also begun using it for neuraxial placement such as with epidurals, spinals, or combined spinal epidurals (CSEs). Several researchers such as Carvalho, Vallejo, Chin, Balki, Ansari, and others have explored the use of ultrasound guidance in obstetric patients and found it useful in several ways such as estimating the distance to and more easily locating the epidural space. We hope to continue to expand the current research in this area.

There have been no attempts to date at West Penn Hospital to begin enrolling patients for this study. This was due to the PI (myself) no longer being available at that facility to conduct the research. The PI at that location has since been changed to [name] and they intend to begin data collection within the next month.

**Significance: Why is it important that this research be conducted? What gaps in existing information or knowledge is this research intended to fill?**

Several studies have looked into the use of ultrasound guidance to assist with placing labor epidurals. It has been demonstrated that ultrasound guidance can help to identify the depth from the surface of the skin to the epidural space thus aiding in epidural placement. Further studies have demonstrated the use of ultrasound guidance in identifying the correct spinal level for epidural placement and in helping to provide more reliable landmarks for placement of the epidural needle. Studies have also been conducted on the use of ultrasound in patients with easily palpable spines and reports of using it in patients that are known to be difficult. Ultrasound use has even been shown to improve complications such as decreasing the failed labor epidural rate in resident trainees.

Despite these studies demonstrating clinical benefits to the use of ultrasound guidance, there have been no studies directly comparing the two methods with a focus on the practical aspects of overall time to perform the procedure, complication rate, and patient satisfaction in morbidly obese parturients. By comparing the use of ultrasound guidance to the current standard of palpation only, we hope to provide evidence that the use of ultrasound in morbidly obese patients provides not just an experimental but also practical advantage over palpation alone, which can then be used to promote the more routine use of ultrasound guidance in this patient population.

**Will screening procedures (i.e., procedures to determine research subject eligibility) be performed specifically for the purpose of this research study?**

\* Yes

**List the screening procedures that will be performed for the purpose of this research study.**

Obese patients will have their medical records screened for eligibility. Additional information for screening will be obtained by history and physical examination which is a routine part of clinical anesthesia care on the labor and delivery unit. Information to be gleaned include BMI and any relevant associated medical conditions which may be a contraindication to epidural placement. After this initial conversation, should the patient be eligible, the study will be introduced in its entirety as explained elsewhere in this protocol.

**Provide a detailed description of all research activities (e.g., all drugs or devices; psychosocial interventions or measures) that will be performed for the purpose of this research study.**

This description of activities should be complete and of sufficient detail to permit an assessment of associated risks.

At a minimum the description should include:

all research activities

personnel (by role) performing the procedures

location of procedures

duration of procedures

timeline of study procedures

This study is to be a prospective, randomized, controlled trial of morbidly obese parturients presenting to either West Penn Hospital or Magee Women's Hospital for delivery and desiring epidural anesthesia. Patients will be screened for participation in the study during the standard pre-anesthesia assessment that is already conducted by anesthesia staff on all patients presenting to Labor and Delivery. Screening will include an evaluation of the patient's medical history and BMI. The study will then be explained to patients who satisfy the inclusion and exclusion criteria and informed consent obtained should they choose to participate. A waiting period of 5-30 minutes will elapse between introduction of the study to the participant's consent to participate. At the time the patient is ready to receive their epidural, an opaque, sealed, numeric envelope labeled only with a study number will be opened containing the data collection sheet and randomly assigned group for that participant. These envelopes will be prepared prior to beginning the study by a healthcare provider not involved in the study. An online randomizer (Randomization.org) will be used to generate a random order for assignment to either the ultrasound guidance group (experimental group) or the palpation only group (control group) which will be revealed to the experimenters only upon opening the envelope at the time of epidural request. These envelopes will be distributed in equal numbers to each facility participating in the study at the onset of the study.

Once the patient has progressed in their labor to the point where they request placement of labor epidural analgesia, the primary investigator for that site ([name] at Magee, and [name] and West Penn) will be the one to open the envelope revealing which group the patient has been assigned to. This will occur during the same hospitalization as the screening visit and in many cases within just a matter of minutes to hours after the initial screening and consent process. This same person will then position the patient in

their labor and delivery room appropriately for their epidural and then use either the ultrasound machine (experimental group) or palpation (control group) to mark with a marking pen the desired location for epidural placement. [name] and [name] will be the only providers to mark the patients. Every attempt will be made for them to be available for study patients, but if they cannot be (they are caring for another patient or are no longer in the hospital at the time the epidural is requested) then the patient may have to be dropped from the study. Once the patient has been marked, a second anesthesia provider who will be performing the epidural will come into the room. This second provider will be blinded to whether the marks on the patient were made based upon ultrasound guidance or palpation (the patient will not be blinded). This second provider who will perform the epidural can be any type of experienced provider (attending, fellow, resident, or CRNA) who has already completed at least 40 epidurals in the past. They will then perform the epidural in the standard fashion, using the previously marked site as their initial entry point. If entering at the already marked site does not result in success, the provider performing the procedure may reassess and redirect at their discretion. During epidural placement, the primary investigator ([name] or [name]) will be responsible for timing the procedure and recording the number of attempts required to succeed. Epidurals are typically placed successfully within 5-10 minutes depending on patient anatomy and provider experience.

Following the epidural placement and achievement of pain relief, the patient will be asked to rate their satisfaction and anxiety levels during the procedure. No extra interventions or monitoring specific to this study (i.e. outside of what is already normally performed) will be required.

Patients will be followed up on in their hospital room within 24 hours of their delivery to assess for any complications related to their epidural placement and to administer the modified WOMBLSQ questionnaire. If a complication is detected, treatment will be given as clinically warranted. Following that visit no further participation from the patient will be necessary. This study is projected to take about 6 months to complete.

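### Envelopes are split equally by count between two hospitals, but balance of the arms within a hospital is neither ensured nor described, and the analysis has no site term

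*Protocol*

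**What the plan says.** The protocol's Study Design section gives the trial as "Prospective, multicenter (MWH and West Penn Hospital) randomized controlled trial". The description of research activities, which follows the screening-procedures heading, sets out allocation in three steps:

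- Generation: "An online randomizer (Randomization.org) will be used to generate a random order for assignment to either the ultrasound guidance group" or the palpation group.
- Preparation: "These envelopes will be prepared prior to beginning the study by a healthcare provider not involved in the study".
- Distribution: "These envelopes will be distributed in equal numbers to each facility participating in the study at the onset of the study".

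No block size, stratum or site-specific list is mentioned, and there is no rule for a stack that runs out or is left unused.

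At each hospital the site's primary investigator "will be the one to open the envelope revealing which group the patient has been assigned to". That person then positions and marks the patient, times the procedure and counts the attempts. The two site investigators "will be the only providers to mark the patients".

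On enrolment, the protocol's Background section reports: "There have been no attempts to date at West Penn Hospital to begin enrolling patients for this study". It adds that the investigator there has changed and that data collection is intended to start within a month.

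The SAP defines the primary outcome as locating time plus catheter placement time. It lists only unadjusted comparisons (t-test, rank tests, Fisher's exact test). Site appears in none of them.

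**The concern.** An equal number of envelopes per hospital is easily mistaken for equal arms per hospital. If a pooled list is dealt out by count, even a list with exactly half in each arm is balanced only over the two stacks together, and only once both are used up. The two sites are starting at different times, so that cannot be taken for granted.

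Site matters more than usual here. Site and marker are the same variable, and the marker's locating time is part of the primary outcome. The same person holds the stopwatch. The mix of providers who place the epidural (attending, fellow, resident or CRNA) may also differ between hospitals. If ultrasound is over-represented at the slower or faster hospital, part of the site difference appears in the arm difference, and the planned tests do nothing to remove it.

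**Working it through.** The documents state no sample size, SD or allocation count, so there is no figure of the plan's own to reproduce. What follows is a range under stated assumptions.

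**Inputs from the documents.** Two sites; envelopes split equally; planning difference 6 min, 80% power, two-sided alpha 0.05 (SAP).

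**Assumptions.** Total envelopes N = 40, 60, 100 or 150. For scale, SDs of 8, 10 and 12 min would require totals of 56, 88 and 126 for 6 min at 80% power. The difference between sites in mean total time, D, is taken as 5 min and as 2 min; the documents support no particular value.

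**Step 1: split within a site.** Each site receives m = N/2 envelopes, of which k are ultrasound. If the pooled list holds exactly N/2 per arm, k is hypergeometric (m drawn from N, of which N/2 are ultrasound). If each envelope is an independent coin toss, k is Binomial(m, 0.5).

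| N | m | 95% range of k, balanced list | P(60:40 or worse), balanced list | P(60:40 or worse), coin toss |
|---|---|---|---|---|
| 40 | 20 | 7–13 | 34% | 50% |
| 60 | 30 | 11–19 | 20% | 36% |
| 100 | 50 | 20–30 | 7% | 20% |
| 150 | 75 | 32–43 | 2% | 11% |

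**Step 2: shift in the crude arm difference.** For a balanced pooled list with all envelopes used, the share of the ultrasound arm at site A is k/m and the share of the control arm there is (m − k)/m. The shift is D × (2k − m)/m. At N = 40, k = 13 and D = 5, it is 5 × 6/20 = 1.5 min.

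| N | Mean absolute shift, D = 5 | Upper 95% limit, D = 5 | Mean absolute shift, D = 2 | Upper 95% limit, D = 2 |
|---|---|---|---|---|
| 40 | 0.62 min | 1.5 min | 0.25 min | 0.60 min |
| 60 | 0.51 | 1.3 | 0.20 | 0.53 |
| 100 | 0.40 | 1.0 | 0.16 | 0.40 |
| 150 | 0.33 | 0.7 | 0.13 | 0.29 |

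The shift is proportional to D, so the D = 2 columns are 2/5 = 40% of the D = 5 columns.

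**Step 3: comparison with sampling error.** A trial sized as the SAP states has a standard error of about 6/(1.96 + 0.84) = 2.1 min. At D = 5 the mean absolute shift is 0.33/2.14 = 15% to 0.62/2.14 = 29% of one standard error.

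**Step 4: only one site enrols.** Site differences then drop out, and the within-site split becomes the split for the whole trial. A 60:40 split has relative efficiency 4 × 0.6 × 0.4 = 0.96, which lowers power from 80% to 78.4%. At 65:35 it falls to 76.2%.

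**Step 5: blocked list per site.** The arm difference at a site can never exceed half the largest block: 2 patients with blocks of 4, 3 with blocks of 6. This holds whatever the other site enrols.

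**The case against.** The strongest reply is that unstratified randomisation is valid. A chance imbalance between sites is not bias; it is part of the random error that the test's standard error already reflects. Steps 3 and 4 support this: the typical shift is a fraction of a standard error, and the loss of power is small. That stands, and it limits how much weight the point can carry.

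A reader might infer that the plan leaves the arms unbalanced within each hospital. The documents do not support that. They are silent on blocking and on lists per site; they do not exclude either. What can be said is that balance is not ensured or described.

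A reader might also infer that West Penn will never use its stack. The same Background paragraph says that data collection there is intended within a month. The documents show an unequal start, not a failed site.

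The 5-minute site difference is open to challenge. The protocol puts typical placement at 5–10 minutes, so 5 min equals the whole width of that range, although total time also includes locating the site. It is best read as a high value, which is why 2 min is shown beside it.

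Finally, blocking has a price. The site investigator sees every earlier allocation at that hospital, and a patient may be dropped if that person is unavailable. Partly predictable assignments in those hands are a real drawback. Varying, undisclosed block sizes reduce it but do not remove it.

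**Conclusion.** The point holds as a gap in the design that is cheap to close. The stated procedure equalises envelopes per hospital and does not secure balance of arms within a hospital, or overall if one hospital under-enrols. The planned analysis does not take site into account, although site coincides with the person who marks and times. The consequence is added noise in the comparison of total time. It does not undermine the randomisation, and a reader who concluded that the primary comparison is biased would be going beyond the documents.

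The size is modest: an average shift of about 0.6 to 0.3 min over 40 to 150 envelopes, with an upper 95% limit of 1.5 to 0.7 min, against a planning difference of 6 min. This rests on a balanced pooled list, both stacks fully used and a 5-minute site difference, none of which the documents state. At 2 minutes the figures are 40% as large. With coin-toss allocation, imbalance is more frequent.

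**What to change.** 1. State in the protocol how the list was generated. If it is already blocked by site, a sentence saying so settles the allocation part of this point.
2. Otherwise, for envelopes not yet opened, replace the shared list with a separate list for each hospital in permuted blocks of randomly varying size (for example 4 and 6). The same uninvolved provider should prepare them, and block sizes should be withheld from both site investigators. On the Background section's account, West Penn's whole stack can be replaced before its first envelope is opened. At Magee the change applies from the next unused number.
3. Add site to the primary analysis in the SAP: a linear model with arm and site in place of the t-test, or a site-stratified rank test (van Elteren) if the data are not normal. This also covers any imbalance already accrued at Magee, which new envelopes cannot correct.

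The cost is regenerating the lists, restuffing the unused envelopes, and a sentence each in the protocol and SAP. No extra patients or staff are needed. The downside is the partial predictability of some block ends to an unblinded site investigator. If that is judged the greater risk, the third step alone still deals with site differences in the comparison, but does not secure the balance.
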